**Figure 2**

PVT, SRT and complete an end of study questionnaire. The questionnaire will inquire about acceptability and tests of blinding.

**Participant Compensation and Safety.** All individuals who complete the study will receive a \$50 -gift card for their time and participation. All participants will be encouraged to report any adverse events (AE) to study staff during and after their participation in the study (i.e., up to 24 hours afterwards) and a physician ([name]) is available if needed. However, the half-life of consumed CBD is approximately 17 hours. The PI will report AEs to the WVU Institutional Review Board (IRB). All study personnel will have completed Human Subjects Training and the PI will obtain WVU IRB approval prior to study inception. As part of the inclusion criteria of the study, participants will be required to have a friend take them home after testing or they must agree to be transported home by study staff. We will also advise all study participants not to drive 24 hours post-testing for safety purposes.

**Data Collection, Management and Analysis.** All collected data will be entered by study staff into the secure, de-identified database and maintained in accordance with WVU IRB and Information Technology. All analyses will be performed in SAS (Cary, NC). The variables to be collected and their source are summarized in **Table 2**. Missing data will be multiply imputed to allow inclusion of all participants regardless of compliance. We will perform both an intent-to-treat analysis based on initial assignment and a protocol analysis, excluding those who fail to complete the study. Both between and within-group analyses will be conducted. Demographic characteristics and driving habits will be compared between groups via descriptive statistics to ensure proper randomization; we will also investigate

tests of blinding by comparing accuracy of group assignment (perceived group assignment will be asked on end of study survey). If differences are noted, models can be adjusted. For between group effects, the data will be compared using Student's T-tests and/or ANOVA for continuous variables if the data are normally distributed; if non-normally distributed a Mann-Whitney test may be utilized. For within group effects, the data will be compared using paired Student's T-tests (for normally distributed continuous paired observations ) or Wilcoxon signed-rank test (for those continuous paired observations not normally distributed). We will perform a correlation using Pearson's R test between the variables collected for Aims 1 and 2, both between and within groups, to assess whether driving performance is

**Table 2. Overview of proposed variables to be collected and for CBD studya**

Aim	Variables	Source
	Socio-demographics, driving history, health	Baseline questionnaire
Aim 1. Determine the effects of CBD on the driving performance of healthy adults aged 18-30 years.	
Driving performance
 
 
Number of lane departures
 
Number of collisions
 
Mean brake reaction time to stimuli
 
Mean standard deviation of lateral position in lane under consistent speed
 
	Driving simulation
Aim 2. Determine the effects of CBD on participants psychological status and cognitive function.	
Sedation
 
 
Self-reported sleepiness
 
Mental sedation: Sum of scores from questions 1,4,11,13 on VAMS—higher scores indicate more mental sedation
 
Physical sedation: Sum of scores from questions 3,5,6,16 on VAMS—higher scores indicate more physical sedation
 
 
Cognitive function
 
 
Number of symbols completed within 60 seconds
 
Number of correct symbols completed within 60 seconds
 
Time to accurately complete Part A and Part B
 
Mean reaction time to stimuli
 
Mean reaction time to stimuli
 
	
SSS VAMS
 
VAMS
 
DSST
 
TMT
 
PVT SRT

Aim 3. Determine the relation of driving performance to changes in psychological and cognitive status.	Correlation between variables in Aims 1 and 2	Driving simulation outcomes, SSS, VAMS, DSST, TMT, PVT, SRT

a: All measures will be assessed between treatment and placebo groups. DSST, SSS, TMT, PVT, SRT and VAMS scores will also be compared within subjects to gauge changes overtime.

correlated with psychological or cognitive testing measures. Data will also be analyzed via sex as well.

As one can see, there is minimal risk to participants. There is no direct benefit to participants. However, there are potential benefits to society that offset the potential risks of this study, which are minimal. The findings of this study will be extremely informative to the public, medical providers, policy makers, and public health practitioners.

Cannabidiol is commonly used drug, yet its effects in healthy populations are virtually unknown. Thus, the risk vs. benefit is reasonable.

### Target Population & Recruitment Methods

Our sample size is 40 individuals. We chose this number based on an a priori power analysis.

Our inclusion and exclusions criteria are as follows: 1) the participant must be currently enrolled as a WVU student, 2) be 18-30 years of age at time of study, 3) have a current drivers' license issued from any state in the United States, 4) has driven at least once in the past 30 days 5) is able to speak and read English, 6) is willing to be randomized and comply with study requirements including a urine drug test on the day they consent to participate in the experiment and complete a test drive to ensure the absence of simulation sickness, 7) not currently taking any daily prescription medications other than birth control, 8) have not been diagnosed with any serious chronic disease by a licensed healthcare provider (including but not limited to Alzheimer's and related dementias, Parkinson's disease or other neurodegenerative disorder, major depressive or anxiety disorder, schizophrenia or other serious mental illness, arrhythmias, cataracts, glaucoma, chronic obstructive pulmonary disease, diabetes, epilepsy, sleep apnea, and fibromyalgia), and 9) has an individual able to drive them home after testing or is willing to be driven home by study staff after testing completion.

Participants will be excluded if they 1) currently smoke or use tobacco products, 2) have used illegal drugs (including cocaine/crack, heroin, methamphetamine, 3,4-methylenedioxy-methamphetamine, inhalants, phencyclidine, lysergic acid, mushrooms, or marijuana) in the past 30 days, 3) has consumed CBD in the past 7 days, or 4) is currently pregnant or lactating. The health conditions and substances noted above have all been associated with changes in driving ability or performance. Also, limiting participants to those who are currently not using illegal drugs, tobacco products, and prescription medications may help minimize bias potentially caused by drug interactions with CBD or known impediments to driving performance from the medications themselves.

Thus, we needed to specify the inclusion and exclusion criteria to avoid confounding. We wanted a healthy population of drivers (i.e., not on medications nor without complex health conditions) to minimize confounding. Drivers older than 30 will probably be more likely to take medications and/or be diagnosed with a chronic condition. As long as a student meets the inclusion and exclusion criteria, they will be able to participate. Thus, we will not limit anyone by gender or race. As mentioned previously, we will recruit via flyers/posters and via emails to the student body. All study advertisement will state that this is a research project conducted by the Department of Epidemiology, the PI's contact information will be included along with the time commitment, inclusion/exclusion criteria, voluntary participation and that the WVU IRB approval is on file.

### Risk & Benefit

**Risk** –There is minimal risk to participants. The first concern may be the small risk of a data breaches. However, this should be minimal as participants will be assigned an identification/study number. All other data will be stored on a secure virtual environment maintained by WVU’s Information Technology department that only study personnel will have access to. A second minimal concern is momentary motion sickness from the driving simulator (e.g., simulator sickness); some individuals may report feeling brief nausea from the simulator. It typically clears immediately when the simulation is stopped. If participants experience this, the trial will stop immediately. The third risk involves the CBD itself. CBD comes from the Cannabis Sativa plant that must have <0.3% delta-9-tetrahydrocannabinol (THC) by federal law. THC is the psychoactive component of Cannabis. Thus, the CBD oil can contain very trace amounts of THC; thus, it is theoretically possible that an individual could test positive for THC/marijuana on an administered drug test. The CBD oil obtained for this study will be obtained from Zatural, a CBD manufacturer from Eden, Idaho. Zatural does attempt to remove THC from their product. The CBD oil will be tested by Botanacor Laboratories (Denver, CO) for microbials, potency, heavy metals, trace THC, pesticides, and residual solvents to ensure purity, label accuracy, compliance, and safety. Testing of the product has shown that it is free of microbials, heavy metals, pesticides, and residual solvents. Potency tests have shown that the concentration of CBD is accurate and that THC and THCa (a chemical precursor of THC) were not detected by this test’s level of quantitation. Trace THC tests, which have a very low level of quantitation (i.e., 0.001%), detected no THCa, and 0.006% THC, which is well below acceptable limits (legal limit is 0.3%). Copies of laboratory reports will be maintained on premise. There are additional minimal risks with the CBD itself. Very little research exists on the effects of CBD even though it is a legal product. The CBD used in this study is a nutraceutical and it is not regulated by the United States Food and Drug Administration. The United States Food and Drug Administration does regulate Epidiolex, which is the prescription version of CBD oil prescribed to treat seizure disorders. According to the package insert for Epidiolex (available at:

[https://www.accessdata.fda.gov/drugsatfda\\_docs/label/2018/210365lbl.pdf](https://www.accessdata.fda.gov/drugsatfda_docs/label/2018/210365lbl.pdf)) and the United States Food and Drug Administration website (available at: <https://www.fda.gov/consumers/consumer-updates/what-you-need-know-and-what-were-working-find-out-about-products-containing-cannabis-or-cannabis>), several side effects of prescription CBD oil have been noted and could potentially harm participants. Prescription CBD oil can cause liver injury/hepatic dysfunction by elevating liver enzymes such as alanine aminotransferase [ALT] and/or aspartate aminotransferase [AST]). Prescription CBD oil can interact with other drugs or alcohol the participant may be taking potentially resulting in serious side effects. Mainly, using CBD oil with alcohol or other drugs, especially those used to treat anxiety, panic, stress, or sleep disorders, could slow brain activity, and increase the risk of sedation and/or drowsiness, which could lead to injury. Prescription CBD oil has also been shown to impact the gastrointestinal tract with side effects such as decreased appetite, diarrhea, weight loss, gastroenteritis, and abdominal pain/discomfort. Prescription CBD oil has also been shown to affect the nervous system and cause somnolence (drowsiness or sleepiness), lethargy, fatigue, malaise, insomnia, poor sleep quality, irritability, agitation, aggression, anger, drooling, or gait disturbances. Anti-epileptic drugs, such as prescription CBD oil, have been associated with suicidal behavior and/or suicide ideation. Prescription CBD oil has also caused hypersensitivity reactions, rashes, hypoxia, respiratory failure, and infection. Studies in animals exposed to CBD oil have also shown male reproductive toxicity, or damage to fertility in males or male off-spring of women who have been exposed to CBD oil. For this study, we are using 300 mg of CBD which is a relatively small dose. This dosage was chosen as it has been used in other studies consisting of both healthy and clinical populations and is generally well-tolerated with no major adverse events; most studies use 150-600 mg, while some have used >1,200 mg.

**Benefit** –There is no direct benefit to participants. However, there are potential benefits to society that offset the potential risks of this study, which are minimal. The findings of this study will be extremely informative to the public, medical providers, policy makers, and public health practitioners. Cannabidiol is commonly used nutraceutical, yet its effects in healthy populations are virtually unknown. Thus, the risk vs. benefit is reasonable.

## Statistical Analysis Plan

All collected data will be entered by study staff into the secure, de-identified database and maintained in accordance with WVU IRB. All analyses will be performed in SAS (Cary, NC). The primary outcome of this study will be driving performance, including number of lane departures, standard deviation of lateral position (i.e., weaving), mean brake reaction time, and number of collisions (Aim 1). Secondary outcomes will be pre-post changes in well-validated measures of mental sedation (SSS, VAMS) and cognitive function (DSST, TMT, PVT, SRT) (Aim 2). The variables that will be collected and their source are summarized in Table 2. Missing data will be multiply imputed to allow inclusion of all participants regardless of compliance. We will perform both an intent-to-treat analysis based on initial assignment and a protocol

analysis, excluding those who fail to complete the study. Both between and within-group analyses will be conducted. Demographic characteristics will be compared between groups via descriptive statistics to ensure proper randomization; we will also investigate tests of blinding by comparing accuracy of group assignment (perceived group assignment will be asked on end of study survey). For between group effects, the data will be compared using Student's T-tests and/or ANOVA for continuous variables if the data are normally distributed; if non-normally distributed a Mann-Whitney test may be utilized. For within group effects, the data will be compared using paired Student's T-tests (for continuous paired observations which are normally distributed) or Wilcoxon signed-rank test (for continuous paired observations which are not normally distributed). We will perform a correlation using Pearson's R test between the variables collected for Aims 1 and 2, both between and within groups, to assess whether driving performance is correlated with psychological or cognitive testing measures. Data will also be analyzed via sex.

**Sample Size** – We conducted an analysis to ensure adequate sample size and power. The analysis was based on mean reaction time, which is one of the primary outcomes between groups. A total sample size of 26 students with a large effect size of 0.7 and  $\alpha=0.05$  using a two-sided, two-sample equal variance t-test achieves 80% power to reject the null hypothesis of equal means. Thus, our total sample size (N=40) should be more than adequate for this study.

**Data Safety Monitoring** – A Data Safety Monitoring Board will not be appointed for this study unless required.

 Table 2. Overview of proposed variables to be collected and for CBD studya

Aim	Variables	Source
	Socio-demographics, driving history, health	Baseline questionnaire
Aim 1. Determine the effects of CBD on the driving performance of healthy adults aged 18-30 years.	Driving performance 
 
Number of lane departures
 
Number of collisions
 
Mean brake reaction time to stimuli
 
Mean standard deviation of lateral position in lane under consistent speed
 
	Driving simulation
Aim 2. Determine the effects of CBD on participants psychological status and cognitive function.	Sedation 
 
Self-reported sleepiness
 
Mental sedation: Sum of scores from questions 1,4,11,13 on VAMS—higher scores indicate more mental sedation
 
Physical sedation: Sum of scores from questions 3,5,6,16 on VAMS—higher scores indicate more physical sedation
 
 Cognitive function 
 
Number of symbols completed within 60 seconds
 
Number of correct symbols completed within 60 seconds
 
Time to accurately complete Part A and Part B
 
Mean reaction time to stimuli
 
Mean reaction time to stimuli
 
	SSS VAMS VAMS DSST TMT PVT SRT
Aim 3. Determine the relation of driving performance to changes in psychological and cognitive status.	Correlation between variables in Aims 1 and 2	Driving simulation outcomes, SSS, VAMS, DSST, TMT, PVT, SRT

a: All measures will be assessed between treatment and placebo groups. DSST, SSS, TMT, PVT, SRT and VAMS scores will also be compared within subjects to gauge changes overtime.

Study personnel will ensure that potential study participants fully understand study procedures and requirements before signing the consent, stress that they are under no obligation to participate and refusal to enroll in the study will in no way affect their care or university standing, and that they are fully aware that they can withdraw from the study at any time. In addition, all participants and study team members will be encouraged to report any adverse events (AE). The PI will promptly report AEs to the Institutional Review Board according to protocol and Institutional Review Board policies; complete an AE form and grade the AE. If any AE is considered serious and unexpected, the event must be reported to the IRB within 7 days from the time the study team receives knowledge of the event. Likewise, any unanticipated problems that occur will be reported to the Institutional Review Board within 7 days from the time the study team received knowledge of the event. Monitoring of this study will be performed by the PI through annual review. In addition, the PI and other key personnel, will review any adverse events as they may occur in each subject, both during testing and afterward. No significant AEs are anticipated but should any occur the event will be promptly reported to the Institutional Review Board. Any unanticipated or serious AE will require re-evaluation of the risk of the study. Study staff will contact all participants 8-12 hours post testing and approximately 24 hours post testing to ensure no AEs occurred. We will advise all study participants not to drive 24 hours post-testing. As part of the inclusion criteria of the study, participants will need to have a friend escort them home after testing or they must agree to being brought home by study staff. [name] will also be available during testing incase issues arise during testing.

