function, the VAMS, SSS, DSST, PVT, SRT, and TMT will also be administered to participants at baseline (prior to study drug consumption) and following completion of the driving simulation test. The primary outcome of this study will be driving performance, quantified using measures strongly associated with collision risk including number of lane departures, standard deviation of lateral position (i.e., weaving), brake reaction time, and collision occurrence. Secondary outcomes will be pre-post changes in well-validated measures of mental sedation (VAMS, SSS) and cognitive function (DSST, TMT, PVT, SRT). We will also collect baseline demographic, health, and driving history data along with data at the end of the survey to assess participant satisfaction and tests of blinding. The entire protocol for each participant will be completed in one day and should take 4-4.5 hours to complete. We chose a parallel design as opposed to a cross-over design to minimize participant burden (i.e., to avoid 2 testing sessions) and facilitate retention. As CBD is a legal nutraceutical that can be obtained over the counter, and it typically is well-tolerated, this study is minimal risk. All data will be deidentified and stored on a secure server that is compliant with WVU Information Technology (IT) Department. An overview of the protocol is below.

**Study Duration** – 24 months

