## Objectives

The **objective/purpose** of this study is to investigate the effects of CBD on driving performance, psychological status (i.e., mood, sedation, drowsiness), and cognitive function in healthy adults aged 18-30 years. This is because CBD is widely sold and consumed and there is some evidence that it may be sedating; however, this has never been evaluated in healthy adults. The **primary outcome** of this study will be driving performance, quantified using measures strongly associated with collision risk, including number of lane departures, standard deviation of lateral position (i.e., weaving), brake reaction time, and collision occurrence. Driving performance will be assessed using a driving simulator. **Secondary outcomes** will be changes in well-validated measures of mental sedation and cognitive function which includes performance on the VAMS, SSS, TMT, DSST, PVT, SRT. The VAMS and SSS are Likert-type scales which assess mental and physical sedation and sleepiness, respectively, at that moment and time. VAMS consists of 16 questions, while SSS only consists of 1. These measures can be summed with higher scores equating to more sedation. The SSS will be summed with greater perceived sleepiness receiving a larger score, similar to the VAMS. The DSST measures psychomotor speed, attention and working memory by requiring participants to translate numbers into symbols; the test is scored by the degree of completion and accuracy over a timed 90 second period. The TMT measures executive function and consists of two parts; the first part requires participants to connect numbers in ascending order, while the second part requires individuals to connect numbers and letters in sequence. The test is scored by the time it takes to accurately complete each test. Increases in time correlate with greater impairment. PVT and SRT are tests given on a computer tablet. They both measure participants reactions to stimuli.

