## Study Design & Methodology

This is a randomized, parallel-group, double-blind, exploratory two-arm trial to assess the effects of CBD on driving ability along with changes in psychological status (e.g., sedation) and cognitive function. Thus, the data will be collected prospectively. The methodology of the study is below.

**Study Design and Protocol Overview.** We propose a randomized, parallel-group, double-blind, exploratory two-arm trial to assess the effects of CBD on driving ability along with changes in psychological status (i.e., mood, drowsiness, sedation) and cognitive function. Forty healthy West Virginia University (WVU) students will be allocated and randomized to receive: (1) 300 mg of pure CBD oil or (N=20) (2) placebo matched in appearance and taste (N=20). After consuming the study drug, each individual will participate in a 25–35-minute driving simulation, which includes a practice drive and brake reaction test, and their driving performance measured. To assess changes in psychological status (i.e., mood, drowsiness, sedation) and drug impairment-related cognitive function, the VAMS, SSS, DSST, TMT, PVT, SRT will also be administered to participants at baseline (prior to study drug consumption) and following completion of the driving simulation test. The primary outcome of this study will be driving performance, quantified using measures strongly associated with collision risk including number of lane departures, standard deviation of lateral position (i.e. weaving), reaction time, and collision occurrence. Secondary outcomes will be pre-post changes in well-validated measures of mood, drowsiness, mental sedation (VAMS, SSS) and cognitive function (DSST, TMT, PVT, SRT). We will also collect baseline demographic, health (including body mass index), and driving history data, including driving habits, along with data at the end of the survey to assess participant satisfaction and tests of

blinding. The entire protocol will be completed in one day and should take 4-4.5 hours to complete for each participant. We chose a parallel RCT design as opposed to a cross-over RCT to minimize participant burden, while still being able to study both within individual (i.e., test battery results) and between group effects (i.e., simulator and test battery performance).

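### Do four joint primary driving measures, with no rule for reading a mixed result, call for a change to the plan?

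*Combined protocol and SAP*

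**What the plan says.** The Statistical Analysis Plan defines the primary outcome as driving performance and lists its parts: "The primary outcome of this study will be driving performance, including number of lane departures, standard deviation of lateral position", then "mean brake reaction time, and number of collisions (Aim 1". Objectives gives the same four as "measures strongly associated with collision risk, including number of lane departures, standard deviation of lateral position (i.e., weaving), brake reaction time, and collision occurrence". Study Design & Methodology has "number of lane departures, standard deviation of lateral position (i.e. weaving), reaction time, and collision occurrence", and the Research Summary ends its list with "brake reaction time, and collision occurrence".

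The Table 2 footnote adds "All measures will be assessed between treatment and placebo groups". Between-arm comparisons use a t-test or ANOVA, or Mann-Whitney for non-normal data. No section gives a composite, an order of testing, an any-one or all-four criterion, or a multiplicity adjustment.

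The Sample Size paragraph says: "The analysis was based on mean reaction time, which is one of the primary outcomes between groups". It uses a two-sided alpha of 0.05 and does not make that measure decisive. Study Design & Methodology describes the study as a "randomized, parallel-group, double-blind, exploratory two-arm trial to assess the effects of CBD on driving ability".

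**The concern.** Aim 1 asks one question, and four tests answer it. If brake reaction time shows nothing and lane departures give p=0.03, the plan does not say whether CBD has been shown to affect driving. An author could lead with whichever measure crossed 0.05, and the claim would then carry more than a 5% risk of error.

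The labels also vary. Collisions are an occurrence in three sections but a number in the Statistical Analysis Plan and Table 2. Reaction time sometimes appears without the word brake, although two secondary tests (PVT and SRT) also yield a mean reaction time.

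**Working it through.** **Inputs.** Four measures and alpha 0.05 two-sided (Statistical Analysis Plan, Sample Size paragraph); 20 per arm (Study Design & Methodology); d=0.7 (Sample Size paragraph). Assumptions, because the documents are silent: each measure is tested at 0.05, any one significant result counts, and the measures share an equal correlation r.

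**The plan's own figure.** The Sample Size paragraph gives 26 participants in total for 80% power. It does not reproduce. An exact two-sided t-test at d=0.7 needs 33.02 per arm, so 34 per arm or 68 in total. Power is 40.3% with 13 per arm and 57.8% with 20 per arm. This is a separate matter, and the present point does not depend on it. It does explain why the power used below is 58%.

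**False-claim risk with no true effect.**
- Independent measures: 1 − 0.95⁴ = 1 − 0.8145 = 0.185.
- Exactly one hit: 4 × 0.05 × 0.95³ = 0.171. Two or more: 0.185 − 0.171 = 0.014.
- Bound under any dependence: 4 × 0.05 = 0.20.
- Correlated measures, by simulating four t-tests with 20 per arm:

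| r | any p<0.05 | exactly one | two or more |
|---|---|---|---|
| 0.3 | 17.5% | – | – |
| 0.5 | 15.7% | 12.3% | 3.4% |
| 0.7 | 13.3% | – | – |
| 0.9 | 9.5% | 4.1% | 5.4% |

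If collisions are rare, their test is conservative. At an assumed mean of 0.05 per driver, Mann-Whitney has size 0.011, and the independent-case total is 1 − 0.95³ × (1 − 0.011) = 0.152.

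**What the stricter rules cost, at d=0.7 and 20 per arm.**
- *One primary measure.* The chance of a positive primary result is 58%. If all four measures were affected at r=0.5, the chance of at least one hit among four is about 86%.
- *Holm across four.* Power for a measure that alone is affected falls from 58% to about 35% (the first step tests at 0.05/4 = 0.0125). If all four are affected at r=0.5, the chance of any rejection falls from 86% to about 66%.
- *Disregarding an isolated hit.* If one measure is affected, the chance that it and at least one other are significant is about 8% at r=0, 7% at r=0.5 and 4% at r=0.9. This rule also leaves two or three hits without a reading.

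**Labels.** PVT and SRT are secondary, so a reaction time described as one of the primary outcomes can only be brake reaction time. In Study Design & Methodology the shorter term stands in a list of driving measures, and that section says the simulation includes a brake reaction test. For collisions, the Statistical Analysis Plan and both copies of Table 2 agree on a number, from which occurrence (one or more) follows directly.

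**The case for a change.** The strongest case for a change is that an exploratory label is not a reading rule. No section says that the Aim 1 p-values are descriptive. The sample size is justified by power to reject a null hypothesis at 0.05, and the Significance and Benefit sections foresee use by policy makers and in legislation. Naming one primary measure, or stating that all four are reported without a confirmatory claim, would take a sentence and need no new data.

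Much of this stands. The omission is real, the arithmetic is right, and such a sentence would be harmless. But a sample-size calculation does not make a study confirmatory, and the Background describes the product as preliminary data. The objection identifies an unwritten rule, not a stated one that gives a wrong answer. Its remedies also pull in different directions: a single primary gives up sensitivity to effects on the other three measures, an adjustment gives up power on each, and a purely descriptive reading makes no formal claim. Experienced statisticians would choose differently among these for 40 students.

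**Conclusion.** No change follows. The excess error, 18.5% at independence and roughly 9% to 18% for r from 0.9 to 0.3, exists only if any single p<0.05 is read as an effect, and the plan does not say that. The independence figure is also the least likely case, because lane departures and lateral-position variability both reflect lateral control on the same drive. If all four had to be significant, there would be no inflation.

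The protection against selective reading is already present: four named measures, all compared between arms, in a trial called exploratory. A sensible analyst reports all four together with estimates and intervals, and a reader wanting strict control can set each p-value against 0.0125. For a small study seeking signs of impairment, keeping that breadth is a reasonable choice against the losses shown above. The collision wording is clerical and is settled by the Statistical Analysis Plan and Table 2.

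This rests on the exploratory reading. If one significant measure out of four were presented as confirmed impairment, the criticism would apply in full to that report.
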